Official Title: Esophageal Food Impaction (ONEFIT)

NCT#: NCT03305848

Study Protocol and Statistical Analysis Plan

Document Date: July 26, 2017

Participant Contact Project Narrative

1. Summary

A piece of food stuck in the esophagus (the tube connecting the mouth to the stomach) is a relatively common occurrence, estimated at a rate of 13 episodes per 100,000 people per year, mostly men, and usually attributed to swallowed meat. The current standard of care for patients presenting to an Emergency Department with this problem includes a trial of medication, usually glucagon but sometimes a carbonated beverage, an injection of nitroglycerin, or benzodiazepines. The medical interventions mentioned above have not been shown to be significantly effective and have unwanted side effects; glucagon is known to cause nausea and vomiting and benzodiazepines can cause sedation and depressed breathing. If the medication fails to relieve the problem, the patient may require a procedure called endoscopy, where a video scope and retrieval tool are inserted into the esophagus to remove the piece of food. There is significant risk associated with endoscopy, including the risks of anesthesia as well as with the physical procedure itself. Endoscopy also results in a prolonged hospital stay due to the time required for the procedure, as well as from anesthesia recovery. The ideal treatment would be a safe, inexpensive, quickly effective medication without significant side effects that could be administered without sedation or extensive monitoring. Oral nitroglycerin solution might just be that intervention.

2. Study aims

Obtain exploratory data on the safety and efficacy of oral nitroglycerin solution for the treatment of esophageal food impaction in a cohort of patients presenting to the ED with presumed esophageal food impaction.

Aim 1: Efficacy. We will determine the success rate of oral nitroglycerin solution in relieving the food impaction by assessing the resolution of symptoms and the ability of the patient to swallow.

Aim 2: Safety. We will calculate the frequency of adverse events from this medical intervention. We are mainly concerned with hypotension, lightheadedness, headache, allergic reaction, dyspnea, vomiting, and pain.

3. Background, Rationale, Significance

Esophageal food impaction is a relatively common illness, estimated to occur at a rate of 13 episodes per 100,000 people per year, mostly men, and usually attributed to swallowed meat bolus. Current standard of care for patients presenting to an Emergency Department with presumed esophageal food impaction includes trial of medical therapy, usually glucagon but sometimes effervescent liquid, sublingual or intravenous nitroglycerin, or benzodiazepines, with a backup of endoscopy for definitive mechanical removal of the food bolus. Glucagon has significant uncomfortable side effects, chiefly nausea and vomiting. The medical interventions mentioned above have not been shown to have significant efficacy; endoscopy is frequently performed after failure of medical management. There is significant risk associated with endoscopy, including the risks of anesthesia as well as with the physical procedure itself. Endoscopy also results in a prolonged hospital stay due to the time required for the procedure, as well as from anesthesia recovery. The ideal treatment would be a safe, inexpensive, quickly effective medical intervention without significant side effects that could be administered without sedation or extensive monitoring. Oral nitroglycerin solution might just be that intervention.

No published trials or case reports using oral nitroglycerin solution for esophageal food impaction were found. Two recent unpublished cases using oral nitroglycerin solution were remarkably and rapidly effective (within 2 minutes) in relieving esophageal food impaction symptoms. The currently proposed study would provide preliminary data which may motivate a larger controlled study.

4. Approach

a. Study design

Prospective, unblinded, single-arm cohort of patients presenting to the Emergency Department with presentation consistent with esophageal food impaction.

b. Population

i. Inclusion/Exclusion Criteria [See Human Subjects items to be moved here]

1. Inclusion Criteria:

- a. Over the age of 18 years
- b. Presentation consistent with esophageal food impaction
- c. Ability to swallow a small volume of liquid.

2. Exclusion Criteria:

- a. Intractable vomiting
- b. Hemodynamic instability or SBP <100 mmHg
- c. Concern for or evidence of significant airway compromise
- d. Concern for or evidence of esophageal perforation,
- e. Concern for or evidence of coronary ischemia
- f. Presentation > 12 hours since onset.

ii. Sample size

1. Convenience sample of 20 patients.

c. Data collection process

i. Process steps for identification of patients or records

1. Study staff may access medical records of all potential subjects' identified (i.e., Workbench) to determine eligibility criteria using information that already exists in the medical record. During this process, no identifiable information may be recorded and any documentation made of a potential subject's information that would disqualify them will be destroyed. If an eligible patient is not being cared for by the PI, study staff must approach the patient's provider to determine if it is appropriate to proceed with the consent process.
2. If additional testing needs to be done to see whether a patient meets criteria for entry into the study, the PI or staff will need to consent the patient first.
3. If the preparation activity confirms a patient is a possible subject, PI/staff approaches the patient to begin the consent process.

ii. Recruitment

1. Study subjects will be recruited from the Emergency Department once their case has been identified as being preliminarily eligible by research assistants or medical providers. Once a potentially eligible patient is identified, the intern and/or CCRC research staff will screen the patient for eligibility based on the inclusion/exclusion criteria. If an eligible patient is identified, research staff will consult with the treating team to determine if the patient is a candidate for enrollment. The research team will use Epic to facilitate the screening process under the preparation for research guidelines. If the patient is eligible and a physician on the study team approves the patient's inclusion into the trial, a member of the research team will approach the patient/family, explain the study verbally, and review the informed consent document. The patient and, if present, legally representative family member, will be given sufficient time to privately review the consent form and discuss potential involvement in the trial. The research team member will again meet with the patient/family to address any questions and discuss enrollment. If appropriate, the research staff member will obtain consent from the patient or family member and begin the enrollment process. Critical Care Research staff is on site and has on-call staff 24/7/365.
2. No recruitment tools will be used in this study.

iii. Consent

1. Study subjects who meet all of the inclusion criteria and none of the exclusion criteria will be approached for consent by study staff prior to enrollment. If an eligible patient is not being cared for by the PI or a Co-I, study staff must approach the patient's provider to determine if it is appropriate to proceed with the consent process. If additional testing needs to be done to see whether a patient meets criteria for entry into the study, the PI, a Co-I, or staff will need to consent the patient first. If the preparation activity confirms a patient is a possible subject, PI/research staff approaches the patient to begin the consent process.

iv. Data sources

1. Study subjects will be interviewed prior to treatment and again after treatment. Medical records from the visit will be collected.
2. Please see attached chart titled "Data Collection Form" describing the variable name, data source, purpose, and measurement scale in the initial application submission

v. Process steps for data acquisition

1. The study subject's demographical, medical, and surgical history, and symptom data will be initially collected from medical record and interview by investigators and/or research assistants during the Emergency Department visit. First at enrollment, then after each administration of study medication. Data will be collected by study investigators and/or research assistants. Data collected includes:
 - Medical record number (MRN), Age, Gender, Visit date, Allergies, Blood pressure, Presenting complaint / HPI, Symptoms throughout the ED visit, medical history, surgical history, time and dose of medications administered
2. The patient's ED provider will be asked for appropriateness for inclusion in the study (yes to any answer will count as an exclusion). They will be asked:
 - a. Is symptoms onset more than 12 hours ago?
 - b. Is there concern for airway obstruction?
 - c. Is there concern for esophageal perforation?
 - d. Is there concern for coronary ischemia?
 - e. Are there any other concerns about including this patient in the study?
3. After discharge of the patient (either from the ED or after admission), their medical record will be accessed for data abstraction by investigators and/or research assistants. The following data will be collected:
 - a. Disposition from the ED
 - b. Length of stay
 - c. Procedures performed during the visit
 - d. Medications given during the visit
 - e. Condition at discharge
4. A single follow-up phone call will be made by investigators and/or research assistants between 4-7 days after discharge to obtain:
 - a. Symptoms at discharge
 - b. Symptoms currently
 - c. Any other treatment required since hospital discharge
 - d. Satisfaction survey

d. *Intervention, treatments*

- i. Up to 3 administrations of 0.4mg sublingual nitroglycerin tablets, dissolved in 10mL tap water, given orally in a single swallow. Each administration is separated by at least 5 minutes, and only if systolic blood pressure > 100 mmHg. The patients then have to pass a swallow test before discharge. The passing of the swallow test will indicate a treatment success. Treatment failure is

defined as lack of symptom resolution 10 minutes after the last dose of nitroglycerin OR inability to tolerate administration OR intolerable side effects.

e. Outcomes/endpoint and other variable definitions, and instruments used

- i. Primary Endpoint is the patient is able to swallow without difficulty within 10 minutes after nitroglycerin administration.
- ii. Secondary endpoint is adverse events during the hospital stay.

f. Statistical analysis plan

- i. Descriptive statistics will be used to summarize the study sample and to evaluate efficacy of the study intervention and frequency of side effects. Specifically, we will first calculate summary statistics (mean \pm standard deviation, frequency counts and percentages) for relevant patient factors (demographics, etc.) at the time of presentation to the ED. We will then calculate the proportion of study patients who achieve resolution of food impaction, with a corresponding 95% confidence interval. Similarly, we will also report frequencies of adverse events, overall and by type of adverse event, along with appropriate measures of variance (including headache frequency and change in blood pressure). Finally we will report outcome statistics (frequency counts and percentages) for repeat symptoms subsequent to the hospital visit (from follow up phone call). Symptom data from follow-up phone call will be used, non-statistically, to identify possible delayed complications of oral nitroglycerin use.

g. Power analysis or statement of precision

- i. No formal hypothesis testing will be pursued, thus we have not conducted a power analysis.. Given the proposed sample size ($n=20$), and projecting 90% success in resolving food impaction (18/20), we anticipate a 95% confidence interval of (68.3%, 98.8%).

h. Strengths and limitations

- i. Strengths
 1. New, promising medical intervention for esophageal food impaction with a strong theoretical likelihood of success.
- ii. Weaknesses
 1. Being a pilot study, further research will need to be undertaken to fully assess the safety and efficacy of the proposed intervention. We will not enroll a comparison group, statistical precision will be limited due to small sample size, and all results will be descriptive (no control for covariates).

5. Setting/Environment/Organizational feasibility

- a. This study is easily achievable, as the study cohort regularly presents to the Emergency Department, the study medication is inexpensive, universally available, and very easily administered.
- b. Research assistants are available 24/7/365 to help with enrollment and data collection.

6. Risks and Benefits

- a. The risks to study subjects are minimal. As with any medication, there is a risk of allergic reaction. Nitroglycerin causes vasodilation and has been associated with modest reduction in blood pressure, however this medication has been safely used for many years. The theoretical systemic absorption of oral nitroglycerin solution is slower than sublingual, and since its half-life is very short, systemic effects may very well be less prominent than with sublingual or intravenous administration.
- b. The benefits to study subjects include potentially rapid reversal of symptoms and food impaction with minimal delay or side effects, avoidance of admission and endoscopy, and avoidance of use of glucagon.

7. Data Confidentiality and Privacy

- a. This study is being conducted in accordance with the ethical principles that are consistent with the ICH and Good Clinical Practice. Once a patient is identified, they are assigned a unique identification number that is assigned to the patient for the duration of the study. The master database linking the patient MRN with the unique identification number is stored on a password-protected, secure share drive housed in the Critical Care Research Center. The CCRC is a locked office with limited accessibility. All

CCRC research staff have EPIC access via a unique user name and password that is monitored by IS&T Security. All research staff are fully trained on the elements of patient privacy, HIPAA and confidentiality.

- b. Because of the protective safeguards in place to protect patient privacy, there is a very low risk to a patient's loss of privacy, risk to reputation or other social risks. The only data that will be accessed from the patient's medical record will be data that is related to the specific admission and meet the defined data abstraction elements.
- c. All eligibility screening, enrollment, randomization, and data entry will take place in the CCRC. The CCRC is a secure, locked department with limited access for security purposes. All patient charts and paper case report forms, including signed consent forms, will be stored in locked file cabinets in the CCRC. A master database linking the subject number and patient name will be maintained on a password-protected server only available to research staff. This is a secure, electronic system that is currently used at Regions Hospital and is approved by IS&T Security. All study data will be coded and de-identified.

8. Timeline

- a. This study is proposed to be completed within 1 year.
 - i. April 2017: IRB Submission
 - ii. May 2017: IRB Approval
 - iii. August 2017: Educate providers and CCRC research staff on enrollment criteria
 - iv. August 2017- August 2018 Enroll patients and collect data
 - v. July 2018 Analyze data and write abstract/manuscript for submission

9. Dissemination/Sharing Results/Integration and Impact

- a. We will prepare the results of the study for publication, with potentially significant impact on routine management of esophageal food impaction by Emergency medical providers.

10. References

- a. Robbins M, Shortsleeve M. Treatment of Acute Esophageal Food Impaction with Glucagon, an Effervescent Agen, and Water. *Am J Roentgenology*. 162:325-28. 1994.
- b. Management of Ingested Foreign Bodies and Food Impactions. *Gastrointestinal Endocscopy*. 73(6):1085-91. 2011.
- c. Ko HH, Enns R. Review of Food Bolus Management. *Can J Gastroenterol*. 22(10):805-8. 2008.
- d. Dellon ES, et al. ACG Clinical Guideline: Evidenced Based Approach to the Diagnosis and Management of Esophageal Eosinophilia and Eosinophilic Esophagitis (EoE). *Am J Gastroenterol*. 108:679-92. 2013.
- e. Weant KA, Weant MP. Safety and Efficacy of Glucagon for the Relief of Acute Esophageal Food Impaction. *Am J Health-Sys Pharm*. 69:573-77. 2012.

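### Patients given standard drugs before dose 1 are neither excluded nor separated, and adverse events are not counted from dose 1, so effects of earlier drugs, above all vomiting, can be attributed to the study solution

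*Combined protocol and SAP*

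**What the plan says.** **Usual care.** Section 3 states that standard care for these patients "includes trial of medical therapy, usually glucagon but sometimes effervescent liquid, sublingual or intravenous nitroglycerin, or benzodiazepines", with endoscopy as the backup. It adds: "Glucagon has significant uncomfortable side effects, chiefly nausea and vomiting". The same paragraph says that no significant efficacy has been demonstrated for these treatments, and section 1 agrees.

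**Eligibility.** Section 4.b.i has three inclusion and six exclusion criteria. The exclusions cover vomiting, haemodynamics, airway, perforation, coronary ischaemia and time ("Presentation > 12 hours since onset"). None mentions drugs already given for the impaction. Section 4.c.v.2 has the provider answer four specific questions and one open question about other concerns, and a yes to any of them excludes the patient. None of the specific questions concerns earlier drugs.

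**Data.** Section 4.c.v.1 collects blood pressure, symptoms and "time and dose of medications administered", at enrolment and after each study dose. Section 4.c.v.3 abstracts the drugs given during the visit from the record.

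**Analysis.** The sample is a "Convenience sample of 20 patients". Section 4.f plans one resolution proportion over all study patients with a 95% confidence interval, and adverse event frequencies overall and by type. Section 4.e defines the safety endpoint over the hospital stay. Aim 2 in section 2 presents these events as effects of the study treatment and names them: "We are mainly concerned with hypotension, lightheadedness, headache, allergic reaction, dyspnea, vomiting, and pain". Section 4.h says that there is no comparison group and no covariate control.

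**The concern.** By the protocol's own account, a patient may have had glucagon, a benzodiazepine, an effervescent liquid or nitroglycerin by another route before the study solution. Such a patient is eligible and is counted in the same way as an untreated one.

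The safety result is the more exposed. Vomiting is the effect that the protocol ascribes to glucagon, and vomiting is on the Aim 2 list. Headache and hypotension are on it too, and earlier nitroglycerin is the same drug by another route. Because the counting window is the hospital stay, an event could be counted against the solution even if it began before the solution was given.

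On efficacy, a late response to an earlier drug would count as a success of the solution. With no comparison group, the pooled proportion alone cannot show this. The study is meant to supply preliminary data for a larger controlled trial, so a misattributed harm or benefit could carry over into that trial's planning.

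**Working it through.** **1. The plan's own figure.** Section 4.g projects 18 successes in 20 and gives an interval of 68.3% to 98.8%. The exact (Clopper-Pearson) interval for 18/20 is 68.3% to 98.8%, so the figure is reproduced. It is 98.8 − 68.3 = 30.5 points wide. Nothing in this point disputes that arithmetic.

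**2. Inputs.** From the documents: n = 20 (4.b.ii) and projected success p = 90% (4.g). Not in the documents, and therefore assumed:
- share pre-treated, s = 25% to 50%;
- chance that the earlier drug itself clears the impaction within the response window, c = 10% to 40%;
- chance that an enrolled pre-treated patient vomits from the earlier drug during the counted period, v = 10% to 40%;
- a less favourable true success rate of 50%, as a sensitivity case.

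**3. Safety.** Expected patients with a vomiting event due to the earlier drug = n × s × v.
- Low: 20 × 0.25 × 0.10 = 0.5 patients, or 2.5% of 20.
- High: 20 × 0.50 × 0.40 = 4 patients, or 20% of 20.

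**4. Efficacy.** Only patients whom the solution would not have helped can become false successes. If the two effects are independent, inflation = s × c × (1 − p).

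| True success p | s = 25%, c = 10% | s = 50%, c = 40% |
|---|---|---|
| 90% (projected) | 0.25 × 0.10 × 0.10 = 0.25 points | 0.50 × 0.40 × 0.10 = 2 points |
| 50% (assumed) | 0.25 × 0.10 × 0.50 = 1.25 points | 0.50 × 0.40 × 0.50 = 10 points |

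At 90%, the upper figure is 0.02 × 20 = 0.4 of one patient, small beside a 30.5-point interval.

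**5. What a split would look like.** Suppose that 18 of 20 succeed.
- With 5 pre-treated (25%), one possible split is 13/15 untreated (exact 95% CI 59.5% to 98.3%) and 5/5 pre-treated (47.8% to 100%).
- With 10 pre-treated (50%), it could be 9/10 in each group (55.5% to 99.7%).

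These intervals show where events fall. They are too wide to compare the groups.

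**The case against.** **The standard drugs may do little.** The protocol says that their efficacy is undemonstrated. If so, c is near the low end or below it, and little success can be borrowed from them. This stands, and it is why efficacy is the lesser part of the point. A reader might infer that the success rate will be materially inflated. That needs both a high c and a true success rate well below the projected 90%, and the documents support neither.

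**Few patients may be pre-treated.** Section 6.b lists sparing patients glucagon as a benefit, which suggests that the solution is meant to come first. Staff are available around the clock, and the open provider question may catch some cases. This could keep s low, but no rule makes it so.

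**The 12-hour limit.** A reader might infer that admitting patients up to 12 hours after onset leaves a long period for earlier treatment. The documents do not support that. The limit concerns time from onset to presentation, whereas the drug trial described in section 3 is care after arrival.

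**Safeguards exist.** Intractable vomiting and systolic pressure below 100 mmHg are exclusions, and each dose requires a pressure above 100 mmHg. Hypotension at entry is therefore largely screened out. Symptoms recorded at enrolment allow events already present to be identified. This stands for the data, but 4.e and 4.f give no instruction to use them in this way. New events after dose 1 in a pre-treated patient remain ambiguous.

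**The bias can be repaired later.** A reader might infer that it could not be seen or removed afterwards. That goes too far: drug times and serial symptoms are collected, so a split could be made. What is missing is prespecification, and in an unblinded cohort of 20 a split chosen after seeing the results would carry little weight.

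**A rule may exist elsewhere.** The Data Collection Form is not in the text supplied, and the criteria heading carries a note about items still to be moved in. This cannot be excluded.

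**Conclusion.** The gap is real, and modest to cheap to close. Nothing in the documents supplied excludes or separates patients treated before dose 1, and the adverse event count has no start at dose 1, although Aim 2 attributes the events to the study treatment. The main exposure is safety, at 0.5 to 4 of 20 patients with misattributed vomiting. The efficacy bias is probably small, at 0.25 to 2 points if the projected 90% is right, and reaches 1.25 to 10 points only if true success is 50%.

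All of these sizes rest on assumed pre-treatment, clearance and vomiting rates. The documents show that carry-over can be counted, not that it will be. Closing the gap would not isolate the drug effect either, because a single arm cannot distinguish spontaneous resolution.

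**What to change.** **Section 4.c.v.1:** add a field recording any drug or effervescent liquid given for this impaction before dose 1, with its time. It should not go in 4.c.v.2, where a yes would exclude the patient. Whether prior treatment should affect eligibility is for the investigators; this change does not alter who is enrolled or how they are treated.

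**Section 4.f, efficacy:** keep the all-patient success proportion with its 95% confidence interval. Prespecify the same proportion with an exact 95% interval by prior treatment (none versus any).

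**Sections 4.e and 4.f, safety:** define the counted adverse events as those that start or worsen after dose 1. Report them overall and by prior treatment, and list events already present before dose 1 separately.

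**Cost:** one data field and two SAP sentences, with the matching wording in 4.e. Medication times and serial symptoms are already planned. The price is small subgroups with wide intervals, so the split should be presented as descriptive. Keeping the all-patient figure preserves the planned denominator of 20.

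### Do the two systolic pressure limits and the two 12-hour checks leave patients with conflicting eligibility or no outcome?

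*Combined protocol and SAP*

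**What the plan says.** **Systolic pressure.** The exclusion list in section 4.b.i removes patients with "Hemodynamic instability or SBP <100 mmHg". Section 4.d sets the dosing condition: "Each administration is separated by at least 5 minutes, and only if systolic blood pressure > 100 mmHg".

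**Twelve hours.** The same exclusion list has "Presentation > 12 hours since onset". In section 4.c.v, item 2, the treating provider is asked "Is symptoms onset more than 12 hours ago", and the rule for those questions is "yes to any answer will count as an exclusion".

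**Outcome.** Section 4.d gives both sides of the result. For success: "The passing of the swallow test will indicate a treatment success". Failure is "defined as lack of symptom resolution 10 minutes after the last dose of nitroglycerin OR inability to tolerate administration OR intolerable side effects". Section 4.e times the primary endpoint from nitroglycerin administration. Section 4.f reports the proportion of study patients with resolution and a 95% interval, without saying whether that means enrolled or dosed patients. Section 4.g projects 18 successes in 20, with an interval of 68.3% to 98.8%, and states that no hypothesis will be tested.

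**The concern.** One limit is below 100 and the other is above 100, so the two do not meet. A patient at exactly 100 mmHg can be consented and counted, yet cannot receive even the first administration while that reading stands. Such a patient has no last dose from which to run the 10-minute clock, has not failed to tolerate anything, and has had no side effects. The denominator is then open: keep the patient as a non-success, or drop the patient. With 20 patients each one is worth 5 points, and the study is unblinded, so a choice made after seeing results is unattractive.

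The 12-hour limit raises a different worry. Someone who arrives 11.5 hours after onset but is screened at 12.5 hours passes the exclusion list and fails the provider question. If the two could not be reconciled, the enrolled population would depend on which page the staff followed.

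**Working it through.** **1. The plan's own figure.** Inputs are x = 18 and n = 20 (section 4.g). The exact (Clopper-Pearson) limits are:

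- lower = 2.5% quantile of Beta(x, n − x + 1) = Beta(18, 3): 68.3%
- upper = 97.5% quantile of Beta(x + 1, n − x) = Beta(19, 2): 98.8%

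This reproduces the stated interval. Its width is 98.8 − 68.3 = 30.5 points.

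**2. Pressure limits side by side.**

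| Reading (mmHg) | Excluded at entry (4.b.i) | May be dosed (4.d) |
|---|---|---|
| below 100 | yes | no |
| exactly 100 | no | no |
| above 100 | no | yes |

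The rules part company at one value only. The dosing rule is the tighter one, so it never permits dosing at a reading that the entry rule bars. A patient dosed at least once whose pressure later falls to 100 or below has a defined outcome, because the clock runs from the last dose actually given.

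**3. How often.** The documents give no pressure distribution, so this rests on assumptions: normal readings recorded to the nearest 1 mmHg. The chance per patient is approximately the normal density at 100, and the chance of at least one in 20 is 1 − (1 − p)^20.

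| Assumed mean / SD | p | At least one in 20 |
|---|---|---|
| 130 / 20 | 0.65% | 12.2% |
| 140 / 22 | 0.35% | 6.7% |
| 150 / 25 | 0.22% | 4.2% |

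Rounding of readings to the nearest ten would raise these chances; a repeat measurement that moves off 100 would lower them.

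**4. How much, if it happens.** Suppose one of 20 enrolled patients is never dosed (exact intervals).

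| Successes among 19 dosed | Patient dropped | Patient kept as non-success | Difference |
|---|---|---|---|
| 18 | 18/19 = 94.7% (74.0 to 99.9) | 18/20 = 90.0% (68.3 to 98.8) | 4.7 points |
| 17 | 17/19 = 89.5% (66.9 to 98.7) | 17/20 = 85.0% (62.1 to 96.8) | 4.5 points |

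In each row, both estimates lie well inside both intervals. A rough expected shift, counting one affected patient, is 0.042 × 4.7 = 0.2 points to 0.122 × 4.7 = 0.6 points.

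**5. Twelve hours.** Both versions start at symptom onset. They differ only in where they stop: arrival, or the moment of asking. Asking cannot precede arrival, so the provider question is at least as strict. A yes to it counts as an exclusion, so the 11.5-hour arrival asked at 12.5 hours is excluded, and the plan gives one answer. That patient is never enrolled, does not enter the denominator, and can be replaced within a convenience sample of 20. The primary proportion does not move.

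**The case for a change.** The best case for acting is that the undosed patient is a wider problem than one reading. Section 4.c.i lets eligibility be judged from data already in the record, and section 4.c.ii gives time for private review before consent. Pressure could be above 100 at screening and at or below 100 when the first dose is due. The provider questions do not ask about blood pressure, and hypotension is the first safety concern named in Aim 2. Read literally, the swallow-test rule does not mention a dose, so an undosed patient whose bolus passed spontaneously might be called a success. A sentence on the denominator would cost almost nothing and would be fixed before the results of an unblinded study are known.

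Much of this stands as description. The denominator is not spelled out, and the failure definition does not cover a patient who was never treated. It does not show that the plan as written would mislead. The swallow-test rule sits in the section on the intervention, and the primary endpoint is timed after nitroglycerin, so an undosed patient cannot meet it. Times and doses of medication are collected for every patient (section 4.c.v), so anyone undosed will be identifiable. A report of a 20-patient cohort can give enrolled and dosed counts, and readers can then form either proportion. Study-physician approval and the provider's open question about other concerns are further checks before enrolment.

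**Conclusion.** No change to the plan follows. The pressure mismatch is real but clerical: the entry and dosing sentences fail to meet at exactly 100 mmHg. They should be reconciled whenever the text is next tidied; I take no view on which limit is clinically right. The 12-hour point does not hold as a conflict, because the any-yes rule settles eligibility and leaves no enrolled patient without an outcome.

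The unstated denominator is a gap in detail that analysts would fill by reporting enrolled and dosed counts. Its size is about 4.5 to 4.7 points per undosed patient in the cases shown, against an interval 30.5 points wide, in a descriptive pilot with no test and no decision threshold. The 4% to 12% chance of a reading of exactly 100 depends on the assumed pressure distributions and on readings recorded to 1 mmHg, and it does not cover patients whose pressure falls between screening and the first dose. The conclusion does not depend on that chance being small, since any undosed patient will be visible in the dosing record and both proportions can be read from the counts. No figure stated in the plan is wrong.
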